#### 6.5.1.6.2 Health-Related Quality of Life

Health related quality of life will be assessed using the Functional Assessment of Cancer Therapy-Hepatobiliary [FACT-Hep; Appendix V]. The FACT-Hep is part of the Functional Assessment of Chronic Illness Therapy (FACIT; 13) measurement system and includes the FACT-General (FACT-G) and an 18-item module specifically designed for patients diagnosed with hepatobiliary carcinomas. The FACT-G is a multidimensional 27-item self-report instrument that measures four dimensions of quality of life including physical well being, social/family well-being, emotional well-being, functional well-being, and overall HRQL. In addition, the FACT-Hep includes a module with 18 additional items specific for patients with hepatobiliary carcinoma. The module includes questions that pertain to symptoms of the disease as well as side effects of the treatment. The FACT-Hep has been demonstrated to be reliable and valid. The internal consistency of the FACT-Hepatobiliary as measured by

Cronbach's alphas was found to be adequate (0.72-0.94) and test-retest reliability ranged between 0.84 to 0.91. Convergent and divergent validity were demonstrated by examining the FACT subscales with scales measuring mood (POMS), social support (ISEL), and social desirability (Marlowe-Crowne Social Desirability Scale). This FACT-Hep will be administered at the following time points:

- screening
- the initial radiation therapy session
- after completing the final radiation treatment
- two months following radiation
- every three months thereafter

#### 6.5.1.6.3 Data Management

The clinical psychologist will manage the prospective data collection and database for the psychosocial data collected at the UPMC Liver Cancer Center. The FACT-Hepatobiliary questionnaire will be administered to patients by telephone interviews. The interviews will be conducted by a trained interviewer with education and training in social sciences. The interviewer will be supervised by a clinical psychologist ([name]). The interviews will take approximately 15-20 minutes to complete at each time point. The interviewer will enter the patients' responses on a secure study website that has been designed specifically to evaluate patient health-related quality of life as part of clinical trials. The data from this website will be imported into SPSS.x".

Once the raw data has been transferred into SPSS.X, the FACT-Hepatobiliary will be scored according to the manual for the Functional Assessment of Chronic Illness Therapy (FACIT; 13). All scales of the FACT are scored so that a high score is good. All negatively phrased questions are reverse scores, and then the items are summed. Items with missing data are prorated using the average of the other response to items on the same scale. Prorated scores can only be calculated if less than 50% of the data is missing (e.g., 3 of 7 items) for a particular subscale or greater than 80% of the data is available for the overall all HROL score. The FACT-G score (overall HRQL) is the sum of the individual subscale scores (physical, social/family, emotional, and functional Total scores for the disease-, treatment, and condition-specific subscales are obtained by summing all subscale scores (physical, social/family, emotional, functional, and additional concerns). To calculate a Trial Outcome Index (TOI), the sum of the physical and functional well-being subscales and the additional concerns subscale is calculated. The TOI is a commonly used endpoint in clinical trials because it is responsive to change, whereas the social/family and emotional well-being subscale scores do not change as quickly over time or have as great of change subsequent to pharmacological treatment. The Functional Assessment of Cancer Therapy-Hepatobiliary Index which consists of 8 items from the FACT-Hepatobiliary will also be calculated.

Minimally Important Difference (MID) scores for all the scales of the FACT have been documented. Combined results from distribution-based analyses and cross-sectional anchor-based methods suggest that clinically meaningful changes are estimated as follows for the FACT-Hepatobiliary: Cancer-specific subscale=2-3; FACT-General=6-7; Hepatobiliary Cancer Scale (HPCS)=5-6; FACT-Hep=8-9; Trial Outcome Index (TOI)=7-8; and FACT-Hepatobiliary Symptom Index (FHSI)=2-3 points.

## 6.6 Study Schema

				SBR	Γ			Follow-up interval: months post therap							rapy					
Assessment	Pre- entry	Fx 1 	Fx 2	Fx 3	Fx 4	Fx 5	2 W	1	2	3	4	5	6	7	8	10	11	13	14	16
History	X	×	X	X	X	X		X	X	X		X			X		Х		x	
Physical exam, vital signs	X	Х	Х	Х	Х	Х		Х	Х	Х		Х			Х		Х		Х	
Karnofsky or ECOG Status	X																			
Height, weight	Х																			
CBC, platelets	X 						X 3	X 	X3	X 	X 	X 	X 							
Chemistries, CMP	X 						X 	X 	X 	X 	X 	X 	X 							
Magnesium,Phosphorus	X 						X 	X 	X 	X 	X 	X 	X 							
Urine or Blood HCG 	Х																			
Fiducial Placement	X 																			
4D FDG-PET/CT Sim	X 																			
FDG-PET/CT or CT	X 								X 			X 			X 		X 			
FACT-HEP Questionnaire	Х	Х				Х			Х			Х			Х		X 			

- After patient is deemed eligible this will be performed within 2 to 3 weeks after screening
   FDG-PET/CT will be performed within 45 days of registration
- 3. Can be done at local lab
- 4. ± 1 week
- 5. 5 10 days post fiducial placement
- 6. Within 14 days prior to registration
- 7. Within 30 days prior to registration 8. Within 14 days of 4D FDG-PET/CT

#### 7.0 Statistical Considerations

#### 7.1 Study Design/Endpoints

The primary objective of this study is to determine the Maximum Tolerated Dose (MTD) and safety of SBRT for liver metastasis using dose escalation. Dose escalation will be via the traditional "up and down" scheme indicated in the two tables below. The traditional up and down study design is a rule-based design which recruits up to 6 patients at each of the 3 dose levels. Patients in cohort(s) of 3 will be entered and the first cohort will be given the lowest dose. The detailed decision rule is in the two Tables below, where there are decisions corresponding to one or more dose limiting toxicities at any given dose level.

- The three dose levels are:
  - 50 Gy in 5 fractions (10 Gy/fx) delivered over a 2-week period.
  - 60 Gy in 5 fractions (12 Gy/fx) delivered over a 2-week period.
  - 75 Gy in 5 fractions (15 Gy/fx) delivered over a 2-week period.

Dose limiting toxicity (DLT) will be defined as any grade III stomach, bowel, liver, or spinal cord toxicity, or any grade IV toxicity as defined by the Radiation Therapy Oncology Group (RTOG). The monitoring and evaluation for dose escalation is referenced below in section 7.3.1. Cohorts of three patients each will be treated at a dose level. Only toxicities observed prior to 7 months after the last fraction of radiation will affect dose escalation.

#### DECISION RULES FOR DOSE LEVEL ESCALATION

Number of patients	Number of	Action
with DLTs at this	patients treated at	
dose level	this dose level	
0	3	Treat 3 patients at the next higher dose level (or add
		3 patients if at the highest dose level).
1	3	Treat 3 additional patients at this dose level.
1	6	Treat 3 patients at the next higher dose level.
>1	3 or 6	Stop dose escalation. Begin de-escalation, or stop the
		trial if at the lowest dose level.

After escalation has stopped, de-escalation will begin at one dose level below the maximum achieved during escalation, and will be carried out according to the table below. The action taken depends on the number of patients previously treated at a dose level. If 3 patients have previously been treated, 3 patients are added; if 6 patients have previously been treated, this level will be declared to be the MTD. The MTD is defined to be the highest dose level at which no more than 1 of 6 treated patient experiences a DLT.

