#### DECISION RULES FOR DOSE LEVEL DE-ESCALATION

Number of	No. of patients	Action
patients with	treated at this	
DLTs at this	dose level	
dose level		
0	3	Treat 3 additional patients at this dose level.
1	3	Treat 3 additional patients at this dose level.
0 or 1	6	Stop de-escalation. The dose at this level is the
		MTD.
>1	3 or 6	De-escalate one dose level, or stop trial if at lowest
		level.

Patients within a cohort need not be accrued or treated at the same time; thus, accrual at a dose level should stop as soon as 2 patients at a dose level have experienced DLT at that level.

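### The de-escalation shortcut in Section 7.1 omits the DLT count, so after late DLTs it can contradict the de-escalation table and the MTD definition

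*Combined protocol and SAP*

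**What the plan says.** The rules are in Section 7.1, in an escalation table, a linking paragraph and a de-escalation table.

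- **Leaving a level.** The escalation table gives the instruction "Treat 3 patients at the next higher dose level" after 0 DLTs in 3 patients or 1 in 6.
- **Pointer to the table.** Once escalation stops, "de-escalation will begin at one dose level below the maximum achieved during escalation, and will be carried out according to the table below". The opening of Section 7.1 also places the detailed decision rule in the two tables.
- **Shortcut.** The linking paragraph continues: "The action taken depends on the number of patients previously treated at a dose level". Then: "If 3 patients have previously been treated, 3 patients are added"; and "if 6 patients have previously been treated, this level will be declared to be the MTD". Neither clause mentions DLTs.
- **Definition.** The paragraph ends: "The MTD is defined to be the highest dose level at which no more than 1 of 6 treated patient experiences a DLT".
- **De-escalation table.** It uses DLTs and patients together. With 0 or 1 DLT in 6, the level is the MTD. With more than 1 in 3 or 6, the trial goes down a level, or ends if already at the lowest.
- **Accrual stop.** Below that table: "accrual at a dose level should stop as soon as 2 patients at a dose level have experienced DLT at that level".
- **Timing.** "Only toxicities observed prior to 7 months after the last fraction of radiation will affect dose escalation". Section 7.2 makes a DLT-free patient evaluable one month after the last fraction. No section says when the escalation decision is taken.

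**The concern.** One paragraph gives two routes to the same decision, and only one of them looks at toxicity. The shortcut is a fair summary of the table if the lower level still has the DLT count at which escalation left it. If a DLT has been added since, the shortcut can call for a different action from the table.

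The MTD is the primary objective, and this sentence can name it. Followed literally in the conflicting state, it would either report as MTD a level that fails the protocol's own definition, or place 3 more patients at a level where the protocol's own accrual stop applies.

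**Working it through.** **1. The two rules side by side, for the level below the one where escalation stopped.**

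| DLTs / treated there | Shortcut | De-escalation table |
|---|---|---|
| 0 or 1 of 3 | add 3 | add 3 |
| 2 or more of 3 | add 3 | go down, or end the trial |
| 0 or 1 of 6 | MTD | MTD |
| 2 or more of 6 | MTD | go down, or end the trial |

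They differ in the second and fourth rows. The second row also breaches the accrual stop, and the fourth also breaches the MTD definition.

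**2. Can those rows be reached?** Escalation leaves a level only at 0/3 or 1/6. If every DLT is known at each decision, these are the only states at a passed level, and the rules never differ. A conflict therefore needs DLTs that appear after escalation: one more at a level left at 1/6, or two at a level left at 0/3.

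**3. Does the plan allow DLTs after escalation?** DLTs count to month 7 and evaluability is at month 1, which leaves 6 months in between. The accrual plan shows whether waiting was budgeted (Section 7.2: at most 18 evaluable patients, at least 6 per year, 3 years):

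- Plan's own figures: 3 levels x 6 = 18 patients; 18 / 6 = 3.0 years = 36 months. Both reproduce, with no waiting between cohorts.
- Six cohorts of 3 have five waits between them. At 1 month each: 36 + 5 = 41 months. At 7 months each: 36 + 35 = 71 months.
- A 12-patient path has three waits. At 7 months each: 24 + 21 = 45 months, still over 36.
- Accrual faster than 6 per year would not rescue the 18-patient case, since five waits alone take 35 of the 36 months.

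Decisions before month 7 are thus the reading that fits the timetable, although the protocol does not state them.

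**4. How often would the rules conflict?** The documents give no DLT rates and no DLT timing, so all inputs except the accrual rate are assumptions.

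- DLT rates across the three levels: 10/20/40%, 15/30/50% and 20/30/40%.
- 50-80% of DLTs within 1 month of the last fraction, the rest by month 7.
- Decisions at 1 month; patients 12 / 6 = 2 months apart on average.
- A conflict is counted if, on first entering de-escalation, the lower level already has 2 or more **known** DLTs.

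Results by simulation:

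| Decision timing | Of trials stopping above the lowest level | Of all trials |
|---|---|---|
| 1 month | about 2-10% | about 2-7% |
| 7 months | 0 | 0 |

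A repeat with the later DLTs spread evenly over months 1 to 7 gave about 2-9% and 1.6-6%.

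**5. Second set of assumptions.** With rates from 5/10/30% to 10/25/50% and 25-75% of DLTs late, the declare-the-MTD conflict arose in 0.5-4.3% of all trials and the add-3 conflict in 0.04-2.8%. Among entries to a level with 6 treated, 6-37% already had 2 or more known DLTs. The event is uncommon overall but not rare where the six-patient clause operates.

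**The case against.** The strongest reply is that the tables govern. Section 7.1 says so at its start, and the sentence before the shortcut says so for de-escalation. To name a level with 2 of 6 as MTD, a reader would have to overlook that pointer, the table row, and the definition that follows directly. Section 8.1 adds monthly review of toxicity together with escalation and de-escalation. This stands as a reason to expect the conflict to be caught. It does not remove it: the shortcut says what the action depends on, leaves DLTs out, and no order of precedence is given.

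A second reply is that the problem derives from the unreconciled 1-month and 7-month periods. That is also right. If each decision waited 7 months, the shortcut would be harmless. The protocol does not say that it does, and the accrual estimate points the other way.

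Two stronger readings are tempting and not supported:

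- **That the design ignores toxicity when it de-escalates.** It does not. The tabulated rule uses the DLT count throughout; the gap is in a summary of it. Nor do the table's rows for 1 or more DLTs in 3 prove that late DLTs were foreseen, since they may simply make the table exhaustive.
- **That the risk is 22-62%.** A reader might compute the chance that a level left at 1/6 ends with 2 or more of 6 by month 7. With true rate p and fraction f of DLTs seen before the decision, q = p(1-f)/(1-pf) and the chance is 1-(1-q)^5. For p = 0.2, f = 0.8: q = 0.04/0.84 = 0.048, giving 22%. For p = 0.3, f = 0.5: q = 0.15/0.85 = 0.176, giving 62%. These count DLTs not yet known when the decision is made, and for those the table declares the MTD too. They also keep all five DLT-free patients at risk, although the first cohort would be largely through its window by then. They do not measure the conflict.

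**Conclusion.** The contradiction is real but narrow. For a level with more than 1 DLT among the 3 or 6 treated, the shortcut and the de-escalation table call for different actions. That state can arise only from DLTs that appear after escalation, which the plan permits.

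Its size is about 2-10% of trials in which escalation stops above the lowest level (about 2-7% of all trials). This rests on the assumed DLT rates, on 50-80% of DLTs falling within 1 month, on 1-month decisions and on 6 patients per year. It is zero if each decision waits 7 months. The case for acting rests less on frequency than on the fact that a stated rule for the primary endpoint can yield an MTD that fails the protocol's own definition, and that correcting it costs almost nothing.

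**What to change.** Reconcile the shortcut wording in the linking paragraph of Section 7.1 with the de-escalation table and the MTD definition, so that one rule applies. One way is to delete the two shortcut sentences and state that the table governs, with the DLT count at the level taken from all DLTs known when the de-escalation decision is made. The sponsor should confirm that the action for each DLT count is the one it intends; this review does not choose it.

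The cost is a wording amendment to one paragraph. It adds no patients, visits or data, and the maximum of 18 is unchanged. With the known DLT count as an input, the chance of declaring as MTD a level with 2 or more known DLTs in 6 is zero by construction. The downside is that in some cases a level would not be declared the MTD, or the trial would end without one, where the present sentence would have named one.

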#### DECISION RULES FOR DOSE LEVEL DE-ESCALATION

Number of	No. of patients	Action
patients with	treated at this	
DLTs at this	dose level	
dose level		
0	3	Treat 3 additional patients at this dose level.
1	3	Treat 3 additional patients at this dose level.
0 or 1	6	Stop de-escalation. The dose at this level is the
		MTD.
>1	3 or 6	De-escalate one dose level, or stop trial if at lowest
		level.

Patients within a cohort need not be accrued or treated at the same time; thus, accrual at a dose level should stop as soon as 2 patients at a dose level have experienced DLT at that level.

#### 7.2 Sample Size/Accrual Rate

The number of patients accrued to the study will depend on the MTD. No more than 18 evaluable patients will be treated in the trial. Based on previous efforts in recruiting patients at the University of Pittsburgh Cancer Institute, it is anticipated that at least 6 patients per year will be enrolled in the protocol and the accrual will be completed within 3 years. An evaluable patient is defined as one who either a) completes the five fractions and has no DLT until one month after the last fraction, or b) a patient who receives at least one fraction and suffers DLT. Patients who are not evaluable will be replaced.

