#### 4.3 Inclusion Criteria

All patients must meet the following criteria in order to be included in this study.

- a. Male or female patients  $\geq 18$  years of age
- b. A life expectancy of at least 6 months with a Karnofsky performance status of at least 70 (Appendix IV)
- c. The target lesion(s) can be accurately measured in at least one dimension according to RECIST and must have a maximum tumor volume of  $\leq 100 \text{ cm}^3$ .
- d. No prior radiotherapy to the upper abdomen.
- e. Previous systemic chemotherapy or non-radiation local therapy (such as surgery, hepatic arterial therapy, chemoembolization, radiofrequency ablation, percutaneous ethanol injection or cryoablation) is allowed. The lesion must however have shown criteria of progression based on RECIST. Local therapy must be completed at least 4 weeks prior to the baseline scan. This is to create a safer treatment environment and to help determine the effect of treatment by SBRT alone. Patients will be allowed to go onto appropriate systemic therapy, as determined by their medical oncologist, 2 weeks following delivery of SBRT.
- f. Patients with resectable disease will be eligible for participation if, and only if, they have comorbidities precluding surgery or refuse to undergo an operation following a multi-disciplinary discussion involving surgical oncology, medical oncology, and radiation oncology. This discussion will actively involve the patient and reinforce that surgery is the current standard of care for such patients.
- g. Cirrhotic status of Child-Pugh class A or B (Appendix I)
- h. Patients can have extra-hepatic disease, provided the hepatic disease is the highest burden, the extra-hepatic disease is low burden and potentially treatable with surgery, ablative radiation therapy, or US Food and Drug Administration—approved first- or second-line systemic therapy regimens.
- i. Patient's will have no evidence of gross vascular invasion.
- j. Patients will have no more than 3 distinct lesions, all being  $\leq$  3cm in greatest dimension, OR 1 lesion  $\leq$  6cm in greatest dimension.
- k. Platelet count  $\geq 60 \times 10^9 / L$ , Hemoglobin  $\geq 8.5 \text{ g/dL}$ , WBC  $\geq 2000 / \mu L$  International normalized ratio (INR) must be  $\leq 2.3$ . Patients who are being therapeutically anticoagulated with an agent such as Coumadin or heparin will be allowed to participate provided that no prior evidence of underlying abnormality in these parameters exists.

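### A patient who leaves between months 1 and 7 without a DLT is scored as a full non-DLT in the MTD count, although the plan's DLT window runs to 7 months

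*Combined protocol and SAP*

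**What the plan says.** Three rules meet here.

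- **Window (7.1).** "Only toxicities observed prior to 7 months after the last fraction of radiation will affect dose escalation".
- **Evaluability (7.2).** A patient is evaluable in one of two ways: one who "completes the five fractions and has no DLT until one month after the last fraction", or "a patient who receives at least one fraction and suffers DLT". Then: "Patients who are not evaluable will be replaced".
- **MTD (decision rules under 7.1).** "The MTD is defined to be the highest dose level at which no more than 1 of 6 treated patient experiences a DLT". Both decision tables count patients treated and patients with a DLT. Neither has an entry for a patient observed for only part of the window.

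On departures, criterion 4.3(b) requires "A life expectancy of at least 6 months with a Karnofsky performance status of at least 70"; the Protocol Summary asks for 3 months. Section 6.3 plans 16 months of follow-up unless otherwise indicated. Section 8.1.1 lists disease progression as a reason for removal, and does not say whether toxicity follow-up continues afterwards. Section 7.3.1 tabulates toxicity grades and describes DLTs, but does not ask how many patients completed the 7 months.

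**The concern.** Take a patient who completes five fractions, passes month 1 without a DLT, and is lost at month 2. Under 7.2 this patient is evaluable, so is not replaced, and fills one of the 3 or 6 places as a non-DLT. Five of the seven months that could have produced a DLT were never observed. A DLT that is seen after month 1 still counts, so only DLT-free leavers are affected.

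Two situations need to be kept apart. After loss or withdrawal, the 7-month outcome is missing. After death from cancer, there are two defensible readings: a competing event, so that the patient is DLT-free by definition, or incomplete observation. The plan chooses neither.

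What is at stake is the primary endpoint. Where a DLT would have followed departure, the error has one direction: fewer DLTs counted, easier escalation and a higher dose named as the MTD. This is separate from when the next dose level opens. Even if every cohort waited the full 7 months, the leaver would still be in the final count as a non-DLT.

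**Working it through.** **The plan's own figure.** "recruits up to 6 patients at each of the 3 dose levels" gives 3 × 6 = 18, which matches "No more than 18 evaluable patients will be treated in the trial". The plan states no target DLT rate, departure rate or operating characteristics, so nothing else can be reproduced.

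**Inputs.** The documents give no rate of loss or withdrawal, so death serves as the worked example of departure. Section 1.1 cites median survival of 10.5 months (microspheres) and of 17 and 20 months (conformal radiotherapy with chemotherapy). Section 1.3 cites 62% alive at 2 years in the metastasis group of an SBRT study. Assumptions not in the documents: exponential survival, DLT timing uniform over 7 months, and departure unrelated to DLT risk.

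**Step 1: departures.** Monthly hazard h = ln 2 / median, or −ln(0.62)/24. The chance that a patient alive at month 1 dies before month 7 is D = 1 − exp(−6h).

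**Step 2: share of DLTs still observed.** r = [1 + (1 − exp(−6h))/h] / 7. The observed DLT risk is p × r, where p is the true 7-month risk.

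| Survival input | h | D | r | At least one leaver in 6, 1 − (1 − D)^6 |
|---|---|---|---|---|
| 62% at 2 years | 0.0199 | 11% | 0.951 | 51% |
| Median 20 months | 0.0347 | 19% | 0.917 | 71% |
| Median 17 months | 0.0408 | 22% | 0.903 | 77% |
| Median 10.5 months | 0.0660 | 33% | 0.851 | 91% |

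**Step 3: effect on the MTD criterion.** P(at most 1 DLT in 6) = (1 − q)^6 + 6q(1 − q)^5, first with q = p, then with q = p × r.

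| True risk p | Fully observed | 62% at 2 years | 20 months | 17 months | 10.5 months |
|---|---|---|---|---|---|
| 10% | 89% | 90% | 90% | 90% | 91% |
| 20% | 66% | 68% | 70% | 70% | 73% |
| 33% | 36% | 39% | 41% | 42% | 46% |
| 40% | 23% | 27% | 29% | 30% | 34% |

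At p = 40% the observed risk is 0.40 × 0.951 = 38% at one end and 0.40 × 0.851 = 34% at the other. If every DLT would occur by month 1, r = 1 and nothing changes.

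**Step 4: would replacing every leaver cure it?** That rule counts all DLTs seen before departure, but only those DLT-free patients who reach month 7. The counted risk becomes p·r / [p·r + (1 − p)·exp(−6h)]. At p = 40%:

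- 62% at 2 years: 0.380 / (0.380 + 0.60 × 0.887) = 42%.
- 10.5 months: 0.340 / (0.340 + 0.60 × 0.673) = 46%.

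P(at most 1 in 6) then falls to 21% and 15%, against 23% when fully observed. Filling 18 places would take 18/(1 − D), about 20 to 27 treated patients.

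**The case against.** The strongest defence is that the two rules can coexist. Section 7.1 may be read as a cap on which toxicities count, not as a demand for 7 months of observation, with 7.2 setting a minimum of one month. The MTD is also defined by patients who experience a DLT among those treated, and a patient who dies of cancer first did not experience one. Under that reading, with death as the only exit, the competing-risk cumulative incidence is simply DLTs over treated patients, which is the count the plan already makes. This stands for cancer death if the plan says so, but it does not. It does not reach loss or withdrawal, where the outcome is unknown, and the cap reading leaves those patients scored as non-DLTs.

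The size is also open to challenge, and fairly. Three of the four survival inputs come from treatments other than SBRT; the SBRT figure gives the smallest effect. Uniform timing has no source in the documents. The toxicity evidence in 1.3 is low (no DLTs up to 60 Gy in 3 fractions in one trial, 10% grade III in another), and at a true risk of 10% the effect is only 1 to 3 percentage points.

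A reader might infer more than the documents support:

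- *That the MTD is shown to be too high.* The direction is conditional on DLTs that would have occurred after departure, and the amount is unknown.
- *That entry survival is shorter than the window.* Criterion 4.3(b) sets a minimum. It makes early departures foreseeable, not typical.
- *That the 7 months were chosen to catch late bowel or liver injury.* No section gives a reason for the length.
- *That replacing every leaver is unbiased and cheap.* Step 4 shows that it errs in the other direction, and section 4.2 allows up to 18 patients.

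**Conclusion.** The point holds in a limited form. As written, 7.2 scores a DLT-free patient who leaves between months 1 and 7 as a completed non-DLT. For loss and withdrawal this treats a missing outcome as tolerance. For cancer death the plan leaves the scoring unstated. Neither the decision tables nor 7.3.1 corrects or discloses it.

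Any resulting error in the DLT rate is downward. Under the assumptions above, the chance of meeting the MTD criterion rises by about 1 to 3 percentage points at a true risk of 10%, 2 to 7 at 20%, 3 to 11 at 33%, and 3 to 10 at 40%. These rises treat cancer death as incomplete observation. If death is declared a competing event, they do not apply to deaths, and only loss and withdrawal remain, at a rate the documents do not give. The point merits a change because it touches the primary endpoint and is easily repaired, not because a large distortion has been shown.

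**What to change.** 1. **Section 7.2.** Reconcile the one-month evaluability rule with the 7-month window in 7.1. For the MTD count, do not treat a DLT-free patient lost or withdrawn before month 7 as a completed non-DLT: either use the existing replacement rule or declare the place incompletely observed.
2. **Section 7.2.** State in advance how death from cancer without a DLT is scored: as a competing event or as incomplete observation.
3. **Section 7.3.1.** For each dose level, report beside the MTD the number followed DLT-free for the full 7 months. Add a 7-month DLT estimate of Kaplan-Meier type that censors DLT-free departures at last observation, with the crude proportion alongside. As an illustration with invented data: two of six patients leave at month 2 and one of the remaining four has a DLT at month 5. The crude proportion is 1/6 = 17%, and the censored estimate is 1/4 = 25%.

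**Cost.** A few sentences and one table. The censored estimate assumes that departures are unrelated to DLT risk, and it is imprecise at 6 patients per level. Replacement adds a few patients. Even when limited to loss and withdrawal it carries some of the overshoot in step 4, in proportion to how many are replaced, so it should not be described as unbiased. Declaring the place incompletely observed needs no extra patients.

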#### 8.0 Data Safety and Recording

#### 8.1 Data safety monitoring plan

All patient data will be collected by the University of Pittsburgh Cancer Institute's Protocol Office. All data will be secured in a password protected file with observance of all applicable HIPAA regulation. A data safety monitoring board will meet monthly to evaluate toxicity for this trial along with dose escalation and de-escalation. Patients/adverse events will be discussed at these monthly disease center meetings. Unexpected serious adverse events will be reported to the IRB and DSMC, and minutes of the monthly disease center meetings will be reviewed at the DSMC meetings.

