#### 8.1.1 Subject Removal Criteria

- 1. Disease progression
- 2. Development of a serious medical illness
- 3. Evidence of dose-limiting toxicity
- 4. Voluntary withdrawal
- 5. Protocol violation
- 6. Discretion of the principal investigator in conjunction with a multi-disciplinary team
- 7. Development of grade 4 toxicity related to experimental therapeutic

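### DLTs count to 7 months but a DLT-free patient is evaluable at 1 month, so a dose level can be cleared, and a 6-patient level declared the MTD, on incomplete windows

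*Combined protocol and SAP*

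**What the plan says.** On which events count, 7.1 states: "Only toxicities observed prior to 7 months after the last fraction of radiation will affect dose escalation".

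On who counts, 7.2 accepts a patient who has a DLT after at least one fraction, or one who "completes the five fractions and has no DLT until one month after the last fraction". It adds: "Patients who are not evaluable will be replaced". A patient who passes month 1 without a DLT and then dies or leaves is therefore evaluable and not replaced.

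On when a decision may be taken, the two tables in 7.1 count patients treated and give no follow-up time. Section 7.1 refers to 7.3.1 for escalation monitoring, but 7.3.1 gives only visits, blood work and grading. Section 8.1 says: "A data safety monitoring board will meet monthly to evaluate toxicity for this trial along with dose escalation and de-escalation". It sets no minimum follow-up.

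On the MTD, the text on de-escalation in 7.1 says that "if 6 patients have previously been treated, this level will be declared to be the MTD". The next sentence reads: "The MTD is defined to be the highest dose level at which no more than 1 of 6 treated patient experiences a DLT". In the de-escalation table, the action for more than 1 DLT among 3 or 6 patients begins: "De-escalate one dose level, or stop trial if at lowest".

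**The concern.** The MTD is the primary endpoint, and it depends on a count of DLTs among patients at a level. The plan has a 7-month limit for the numerator and a 1-month limit for entry to the denominator, with nothing to connect them. Two consequences follow.

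First, the next dose can open while much of the current level's window is still unobserved.

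Second, suppose a level is cleared with 1 DLT in 6, the next level proves too toxic, and a second DLT then appears at the lower level inside its 7 months. The sentence on 6-patient levels names that level the MTD. The definition directly after it and the table do not. Two people applying 7.1 to the same data could report different MTDs. The escalation table is also silent on whether such a late DLT at a lower, cleared level stops escalation.

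Patients who leave after month 1 add to this, because they stay in the count as if their whole window had been DLT-free. Such losses are foreseeable. Section 4.3 asks for a life expectancy of only 6 months, and the first removal criterion in 8.1.1 is "1. Disease progression".

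**Working it through.** **The plan's own figures.** 3 levels × 6 patients = 18; 18 / 6 per year = 3 years. Both figures in 7.2 reproduce, with no pause in accrual.

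**Inputs.** The documents give the 7-month window, 1-month evaluability, cohorts of 3, treatment over 2 weeks (taken as 0.5 month), and at least 6 patients per year (one per 2 months). They give no DLT rate for this regimen and no onset times. I assume a true 7-month rate p of 5% to 30% with constant hazard. Section 1.3 cites no DLTs up to 60 Gy in 3 fractions, which 3.3 calls biologically equivalent to the top dose here, and 10% grade III toxicity in another trial. About 10% or less is therefore the range with some support.

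**Follow-up at a 1-month decision.** Entries at months 0, 2 and 4; the third patient reaches month 1 at 4 + 0.5 + 1 = 5.5. Follow-up is then 5, 3 and 1 months: 9 of 3 × 7 = 21 patient-months (43%). At 12 per year it is 3 + 2 + 1 = 6 of 21 (29%). This step needs no DLT rate.

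**Chance that a level is cleared** (0 of 3, or 1 of 3 and then 1 of 6):

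- Full window: (1−p)³ + 3p(1−p)⁵.
- 1-month decisions: let q_t = 1 − (1−p)^(t/7). If the level expands to 6, the second cohort enters at months 6, 8 and 10 and the decision falls at 11.5, when the first three patients have complete windows. So P = A + B, with A = (1−p)^(9/7) and B = A(q₅+q₃+q₁)(1−p)².

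At p = 10%, the full window gives 0.729 + 0.177 = 0.906. With 1-month decisions, A = 0.873, q₅+q₃+q₁ = 0.0725 + 0.0442 + 0.0149 = 0.132, B = 0.873 × 0.132 × 0.81 = 0.093, and P = 0.966.

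**Cleared levels that later reach 2 or more DLTs.** After 0 of 3, the unobserved months are 2, 4 and 6. At p = 10% the late-DLT probabilities are 0.0297, 0.0584 and 0.0864, so the chance of at least two is 0.0090. After 1 of 6, the second cohort has 12 unobserved patient-months, and the chance of a further DLT is 1 − 0.9^(12/7) = 0.165. The share is (0.873 × 0.0090 + 0.093 × 0.165) / 0.966 = 0.024.

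| True 7-month DLT rate | Cleared, full window | Cleared, 1-month decisions | Of those, 2 or more DLTs in the end |
|---|---|---|---|
| 5% | 97% | 99% | 1% |
| 10% | 91% | 97% | 2% |
| 20% | 71% | 88% | 8% |
| 30% | 49% | 76% | 15% |

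If instead half of the DLTs occur by month 1 and the rest evenly to month 7, the third column becomes 98%, 94%, 82% and 66%.

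**Early leavers alone.** Suppose decisions wait the full 7 months but deaths after month 1 count as DLT-free. With exponential survival, 2-year survival of 62% (an SBRT series in 1.3) gives 1 − 0.62^(6/24) = 11% dying between months 1 and 7. A median of 10.5 months (a microsphere series in 1.1, a different treatment) gives 1 − 2^(−6/10.5) = 33%. Clearing then moves from 91% to 91–93% at p = 10%, from 71% to 73–77% at 20%, and from 49% to 52–58% at 30%.

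**The case against.** The strongest reply is that the two limits can coexist in a rolling design: decide early, and let late DLTs count when they appear. The MTD definition and the de-escalation table point that way. This largely stands, and it is why the harm at supported rates is small. It does not cure the sentence on 6-patient levels, which has no exception, and it cannot recover windows that are never completed.

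Some stronger readings are tempting, and the documents do not support them:

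- *The design is likely to name a wrong or unsafe MTD.* The large differences need DLT rates of 20% to 30%, which no cited result supports. At 10%, escalating is usually the desired outcome, so much of the 6-point gap is fewer false stops.
- *Deaths after month 1 seriously bias escalation.* At 10% they shift it by 0 to 2 points. Nor does the plan say that removal ends toxicity follow-up: 6.3 follows patients for 16 months or until death.
- *The examination gap between months 5 and 8 hides DLTs.* Blood work is monthly for at least six months, serious events are reportable within 24 hours (8.2.1), and the board meets monthly. Only an event missed by all three and first found at month 8 is affected.
- *The 3-year accrual estimate is wrong, or rules out a 7-month wait.* The stated rate is a minimum. At exactly 6 per year, an 18-patient path with a 7-month hold at both dose changes reaches last enrolment at month 45 rather than 34, but 18 is the maximum. On the 12-patient path (3, 3, then 6), entries at 0, 2, 4; 11.5, 13.5, 15.5; and 23 to 33 end at month 33, inside 3 years.

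**Conclusion.** The point holds and should be fixed. As written, a level can be cleared on partial windows, and a 6-patient level can be declared the MTD at 2 of 6 DLTs, against the plan's own definition. This is more than missing detail, because rules followed literally can give a wrong primary result.

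The size is modest at about 10% DLTs: escalation 97% against 91%, with about 2% of cleared levels ending at 2 or more DLTs. At assumed rates of 20% and 30% it is 88% against 71%, and 76% against 49%. The 9 of 21 patient-months rests only on accrual of 6 per year and a decision at month 1. The probabilities also rest on constant hazard and an assumed DLT rate, and the gap narrows if DLTs come early. The documents do not show that a full 7-month wait before each escalation is required.

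**What to change.** 1. In 7.1, declare the MTD only when every patient counted at that level has completed the 7-month window or had a DLT. Report patients who leave earlier without a DLT separately, and do not count them as full DLT-free windows.
2. In 7.1, state that a late DLT within the window at an already cleared level is recounted, so that more than 1 DLT there stops escalation and triggers de-escalation. Say that this overrides the sentence on 6-patient levels.
3. Minor: count DLTs by onset date within the window rather than by date observed.

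**Cost.** The changes are mostly wording. The final MTD call waits up to 7 months after the last patient's treatment, within the 16-month follow-up. A few patients may need replacing: with 11% to 33% dying between months 1 and 7, the expected loss among 6 patients at the MTD level is 6 × 0.11 = 0.7 to 6 × 0.33 = 2.0, before any loss through removal.

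**Left to the sponsor.** The minimum follow-up before the next dose opens should be stated, but its length trades time against early exposure. Whether to replace every early leaver at every level is a similar choice. Neither is needed for items 1 to 3.
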